
Rule3: Subjects present only in Diary data

Night Time Endpoints	
These endpoints need to be reported as the “average” or “mean” for each protocol time point (due to the amount of day or night time not matching a protocol day or night)	
CODE	DESCRIPTION
NNTMTEPHR	Number Night Time Movement Episodes/Hr
NRESTEF	Percent Time Night-time Rest Efficiency
RFRGI	Rest Frag Index=Move Time/Num Movement Episode
AVGDURMTE	Average Duration Movement Episodes
Number Night Time Movement Episodes/Hr. NNTMTEPHR	
Limitations of each 24-hour recording period = the 24-hour recording periods do NOT match protocol days, due to the mixed start times that are governed by the sensor “activation.” (first data recorded by the sensor) – as such reporting the data out by recording day does NOT make sense, the data must be reported over the 3 days for each protocol timepoint (ie data need to be averaged out). A note pertaining to this must be added to any data that lists out the raw data for each recording period.
 
Average number night time movements/hour (Day 1+2+3) divide by 3, ie Day 1 + Day 2 etc. / actual number of recording periods at each time point (sometimes there are more or less values at each protocol time point)

Percent Time Night-time Rest Efficiency NRESTEF	
Core study phase only. Limitations as above
 
Average % time night time rest efficiency (Day 1+2+3 values) divide by 3, ie Day 1 value + Day 2 value etc. / actual number of recording periods at each time point (sometimes there are more or less values at each protocol time point)

Rest Frag Ind=Move Time/Num RFRGI Movement Episode	
Core study phase only. Limitations as above
 
Average night time rest fragmentation index (Day 1+2+3 values) divide by 3, ie Day 1 value + Day 2 value etc. / actual number of recording periods at each time point (sometimes there are more or less values at each protocol time point)

Avg Duration Movement Episodes AVGDURMTE
	
Done for each 24 hours' period But again, need 1 value for protocol time point. An average of the average over 3 days. – Use the number of active periods in the categories above – add up to derive a total, use that total to create a more accurate average.
 
Average duration of movement disorders = values [Day 1 + day 2 + day 3]/total number of night time movements [Days 1+2+3]

---	--

Speech Assessments

The 4 tests for speech assessments are:

- Short ah

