2.92.	FAS	EFF_T1	Summary of Relative Rate of Decline of Rest Fragmentation Index (All data)		SAC
2.93.	FAS	EFF_T1	Summary of Relative Rate of Decline of Rest Fragmentation Index (Quality data)		SAC
2.94.	FAS	EFF_T1	Summary of Monthly Rate of Decline of Rest Fragmentation Index (Quality data)		SAC
2.95.	FAS	EFF_T1	Summary of Average Duration Movement Episodes (All data)		SAC
2.96.	FAS	EFF_T1	Summary of Average Duration Movement Episodes (Quality data)		SAC

CONFIDENTIAL

201283

Efficacy: Tables					
No.	Population	IDSL / TST ID / Example Shell	Title	Programming Notes	Deliverable [Priority]
2.97.	FAS	EFF_T1	Summary of Average Change from Baseline of Duration Movement Episodes (All data)		SAC
2.98.	FAS	EFF_T1	Summary of Average Change from Baseline of Duration Movement Episodes (Quality data)		SAC
2.99.	FAS	EFF_T1	Summary of Relative Rate of Decline of Duration Movement Episodes (All data)		SAC
2.100.	FAS	EFF_T1	Summary of Relative Rate of Decline of Duration Movement Episodes (Quality data)		SAC
2.101.	FAS	EFF_T1	Summary of Monthly Rate of Decline of Duration Movement Episodes (Quality data)		SAC
2.102.	FAS	EFF_T3	Statistical Analysis of Relationship between Absolute Values of Night Rest Endpoints and Absolute Value of Total ALSFRS-R		SAC
2.103.	FAS	EFF_T3	Statistical Analysis of Relationship between Change from Baseline of Night Rest Endpoints and Change from Baseline of Total ALSFRS-R		SAC
2.104.	FAS	EFF_T3	Statistical Analysis of Relationship between Slope of Night Rest Endpoints and Slope of Total ALSFRS-R		SAC

Efficacy: Tables					
No.	Population	IDSL / TST ID / Example Shell	Title	Programming Notes	Deliverable [Priority]
Heart Rate Variability					
2.105.	FAS	EFF_T1	Summary of Mean HRV LF/HF (All data)	Include: 
 • Mean HRV Lying minus active • Mean HRV Lying minus 'sedentary not lying' • Mean HRV Lying (average) • Mean HRV Active(average) • Mean HRV 'sedentary not lying'(average) 	SAC
2.106.	FAS	EFF_T1	Summary of Change from Baseline of Mean HRV LF/HF (All data)	Same as above	SAC
2.107.	FAS	EFF_T1	Summary of Relative Rate of Decline of Mean HRV LF/HF (All data)	Same as above	SAC
2.108.	FAS	EFF_T1	Summary of Monthly Rate of Decline of Mean HRV LF/HF (All data)	Same as above	SAC
2.109.	FAS	EFF_T1	Summary of Mean RMSSD (All data)		SAC
2.110.	FAS	EFF_T1	Summary of Mean RMSSD (Quality data)		SAC
2.111.	FAS	EFF_T1	Summary of Change from Baseline of Mean RMSSD (All data)		SAC

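### Average Duration Movement Episodes is derived as summed nightly averages over a total episode count, so it is not a duration and falls as episodes become more frequent

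*SAP*

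**What the plan says.** The Night Time Endpoints table in SAP Section 9.4.3 lists AVGDURMTE as "Average Duration Movement Episodes". The row says that it is produced for each 24-hour period, so every recording period already carries an average duration.

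The row then asks for a single figure: "But again, need 1 value for protocol time point". It describes this as "An average of the average" over three days, to be made more accurate with a total count. The instruction for that count is: "Use the number of active periods in the categories above".

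The formula follows. Its numerator is "Average duration of movement disorders = values [Day 1 + day 2 + day 3" and its divisor is the total "number of night time movements [Days 1+2+3".

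The neighbouring rows for rest efficiency and rest fragmentation combine nights differently: "ie Day 1 value + Day 2 value etc. / actual number of recording periods at each time point".

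Section 9.11.4 reports the result in Tables 2.95 to 2.101, for example "Summary of Average Duration Movement Episodes (Quality data", and includes it among the night-rest endpoints correlated with total ALSFRS-R in Tables 2.102 to 2.104.

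**The concern.** A pooled mean duration needs total movement time in the numerator, that is, each nightly average multiplied by that night's number of episodes. The formula has no such multiplication. It adds averages and divides by a count of events.

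A wrong scale alone would matter little, because a constant divisor cancels in relative change and in a correlation. Here the divisor is the subject's own episode count, which can differ between subjects and between visits. That count is itself a night-rest measure in Section 2.2, so a change in how often a subject moves would appear as a change in how long each movement lasts.

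The count is also not settled. The sentence before the formula points to the active-period categories, which Section 2.2 starts above 1 minute. The formula points to night-time movements. Section 2.2 lists these as separate measures.

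The study has no primary endpoint (Section 1), and Section 9.8 judges relationships on the strength of the correlation coefficients. For this marker, a misderived variable therefore alters the reported finding directly. It also enters Figures 2.58 to 2.64 and Listings 56 and 57.

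**Working it through.** **Inputs.** The SAP states no figure for this endpoint and no episode counts, so there is nothing to reproduce. Let a_i be the average episode duration on night i (the value supplied per recording period), n_i the number of movement episodes that night, and k the number of nights. All values of a_i and n_i below are assumptions.

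**Formulas.**
- As written: Σa_i / Σn_i
- Count-weighted mean (total movement time over total episodes): Σ(n_i × a_i) / Σn_i
- Simple mean over nights: Σa_i / k

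With the same a and n every night, the written form is ka / kn = a / n. It equals the mean duration only when n = 1.

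**Dependence on the count, duration fixed at 2 min on three nights.**

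| Episodes per night | As written | Count-weighted mean | Simple mean |
|---|---|---|---|
| 1 | 6/3 = 2.0 | 2.0 | 2.0 |
| 5 | 6/15 = 0.40 | 2.0 | 2.0 |
| 10 | 6/30 = 0.20 | 2.0 | 2.0 |
| 20 | 6/60 = 0.10 | 2.0 | 2.0 |
| 40 | 6/120 = 0.05 | 2.0 | 2.0 |

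The written value halves each time the count doubles, although duration does not change.

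**Unequal nights.** Take a = (1, 2, 3) and n = (10, 20, 30).
- As written: 6/60 = 0.10.
- Count-weighted: (10 + 40 + 90)/60 = 2.33.
- Simple mean: 2.0.

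Doubling every count gives 6/120 = 0.05 as written and leaves the other two unchanged.

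**Effect on change from baseline.** Baseline: three nights, 20 episodes a night, 1.5 min each.

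| Scenario | True mean (min) | True change | As written | Change as written |
|---|---|---|---|---|
| Baseline | 1.5 | n/a | 4.5/60 = 0.075 | n/a |
| 30 a night, duration unchanged | 1.5 | 0% | 4.5/90 = 0.050 | -33% |
| 40 a night, duration up 50% | 2.25 | +50% | 6.75/120 = 0.05625 | -25% |

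With equal counts per night, the written value changes by the factor (duration ratio)/(count ratio). A rise in duration is therefore reported as a fall whenever the count rises proportionately more. If both double, for example from 2 min and 10 a night to 4 min and 20 a night, the written value stays at 0.20 and the doubling of duration disappears.

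**The case against.** The strongest defence is that the summed quantity in the numerator is never defined. If it meant each night's total movement time, the formula would be total time over total episodes, a valid pooled mean. Movement time does exist as a quantity, because the Rest Fragmentation Index is labelled as move time over number of episodes. However, the row does not say this and the context points the other way. The endpoint is a per-period average, the row speaks of averaging averages, and the adjacent rows use the same term for the endpoint's own per-period result. The heart rate variability rows of Section 9.4.3 also write out a sum of daily means over a total count. Where movement time is meant, the SAP names it. Even on the generous reading, the row must state its numerator.

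The two counts might also be read as one: add up the active periods, then use that total as the number of movements. The SAP does not define how an active period relates to a movement episode, so their difference is inferred from the separate listing in Section 2.2 and the 1-minute threshold. The mismatch in the text stands, and a programmer would have to guess.

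Two points bear on importance. The Rest Fragmentation Index, as labelled, is itself a mean time per episode and is averaged with a valid divisor, so similar information is reported elsewhere. The study is also exploratory, and this is one of four night-rest endpoints in the derivation table. Both limit the consequences. Neither makes the AVGDURMTE displays correct.

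**Conclusion.** The concern holds. On the plain reading, the time-point value of AVGDURMTE is a sum of nightly averages divided by a total episode count. That is not an average duration, and it moves inversely with episode frequency. The direction of the distortion follows from the formula. Its size depends on episode counts that the SAP does not give. Under the assumed values, the written figure is one twentieth of the mean duration at 20 episodes a night, and a 50% rise in duration can be reported as a 25% fall. Sign reversal is shown to be possible, not likely. The divisor is also named inconsistently within the row. As written, the displays for this endpoint and its correlations with ALSFRS-R would rest on the wrong variable.

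**What to change.** Replace the formula in the AVGDURMTE row of Section 9.4.3 with: the sum over valid nights of (nightly AVGDURMTE × that night's number of night-time movement episodes), divided by the sum of those episode counts over the same nights. This is total movement time over total episodes, and it meets the row's stated aim of a more accurate average. Use the night-time movement episode count in both places, delete the reference to the active-period categories, and change movement disorders to movement episodes. A simple mean over recording periods would also remove the dependence on counts, but it would not weight nights by their number of episodes.

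The cost is SAP wording and one derivation line, with no new data collection. Both inputs are named in Section 2.2. The code list in Section 9.4.3 shows only the per-hour rate (NNTMTEPHR), so the variable holding the raw count must be named there. The change should be made before the affected tables, figures and listings are programmed.

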2.2. Study Objective(s) and Endpoint(s)

Objectives	Endpoints
Exploratory Objectives	Exploratory Endpoints

Explore the application of actigraphy:
 
 • For measuring movement/physical activity in ALS subjects • As a marker of ALS disease progression 	
 • Change over time in measurements of movement/physical activity by accelerometer-reported by day and night time. Measurements include Duration of wear time, (combining day & night values to give Wear time), Overall time spent active, Overall time spent sedentary not lying, Overall time spent lying, Overall time spent sedentary, Time spent with Sensor off, Total Activity Score, the maximum score from a 1 min window in a 24-hour period and 5 x Active Periods (5 categories: >1 to <=2min active up to >30mins active) • Change over time in measurements of night time rest by accelerometer reported endpoints: Percent Time Lying Down (at night), Number Night Time Movement Episodes, Number Night Time Movement Episodes/Hr, Percent Time Night-time Rest Efficiency, Rest Fragmentation Index =Move Time/Num Movement Episode, Average Duration Movement Episodes • Relationship between the ALSFRS and accelerometer measures of movement/activity and night time rest endpoints.

Explore the application of continuous remote monitoring of heart rate measures:
 
 • For measuring autonomic nervous system function in ALS subjects • As a marker of ALS disease progression 	
 • Change over time in heart rate variability (HRV) as measured by a heartbeat sensing electrode. Measurements include: 
 ○ Mean and variance for LF/HF (lying, sedentary not lying, active). ○ Mean and variance for HRV effect of being upright = LF/HF sedentary not lying minus LF/HF lying ○ Mean and variance for HRV effect of activity = LF/HF active minus LF/HF lying ○ Mean and variance for RMSSD (24 hours)

Objectives	Endpoints
	
 • Relationship between the ALSFRS and biotelemetry measures of HRV.

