Sleep = 9 hours, permit 2 hours charging = 7 hours. 60% of 7 hours = 252 mins, 4.2 hours. Exclude data point if active night + sedentary night = <4.2 hours

Night time rest endpoints

Sleep = 9 hours, permit 2 hours charging = 7 hours. 60% of 7 hours = 252 mins, 4.2 hours. Exclude data point if active night + sedentary night = <4.2 hours

Heart Rate Variability (24 hour endpoints only)

The amount of data present over a 24-hour recording period is also important for the 24 hour endpoints for HRV: mean and variance for HRV recorded using RMSSD methods (24 hours). 24-hour RMSSD HRV data with 40% or more data present will be accepted for analysis. The number of time windows that the HRV data is determined from is recorded in the dataset from McLaren. The following data quality rule will be applied:

Number of 5-minute windows (number of data points) in 24 hrs = 288. Allow for 2 hours charging = 24. Leaves 264 data points. Ruling = require 40% or more of data present for the 24-hour time period, otherwise it is not considered as representative of 24 hours. 40% of 264 = 105.6. Therefore, exclude data point if number of 5-minute window (number of data point) < 105.

Speech Endpoints

There is no data quality rule for Speech data as there are no data quality deviators, and all available data will be included in the summary and statistical analysis.

The data quality deviator flags will be populated in the data and the summary tables and figures will be produced for data with the deviator and without the data quality deviator.

[Table 3](#) provides an overview of the planned efficacy analyses, with further details of data displays being presented in [Appendix 11](#): List of Data Displays.

Table 3 Overview of Planned Exploratory Analyses

Endpoint / Parameter/ Display Type	Absolute						Change from Baseline							
	Stats Analysis			Summary		Individual	Stats Analysis			Summary		Individual		
	T	F	L	T	F[1]	F	L	T	F	L	T	F[1]	F	L
Actigraphy - feasibility & Wear time Measures														
Wear Time (active + sedentary time)				Y			Y							
Duration of day time wear time				Y			Y							
Duration of night time wear time				Y			Y							
Actigraphy Diary Data – feasibility measures														
Actigraphy Diary data) (Items 2, 3, 5, 6, 8) And Feasibility				Y			Y							
Device impact Data – feasibility measures														
Device Impact				Y			Y							

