 - Central tendency of fundamental F0, relative jitter, relative shimmer
- Long ah
 - Central tendency of fundamental F0, relative jitter, relative shimmer
- Single word – doily
 - Average phoneme rate, average phonation time
- Running speech (bamboo passage)
 - Speaking rate % pause time

CODE	DESCRIPTION
AA001	Central tendency of fundamental F0 (code 001: short ah) HZ (code 002: long ah) ?? middle five seconds of the phonation interval??
AA002	Relative Jitter (code 001: short ah) % (code 002: long ah)
AA003	Relative Shimmer (code 001: short ah)

%	(code 002: long ah)
AA004 (Hz/s)	Average phoneme rate (Phoneme – subpart of word) code 003: “single word” doily
AA005 (s)	Average phonation time code 003: “single word” doily
AA007 %	% pause time (Code 004: running speech)
AA008 (WPM)	Speaking rate (Code 004: running speech)

Heart Rate Variability (all LF/HF HRV metrics are over 5 minutes’ windows)

HRV data are captured for each of the activity classifiers: Active + Lying + “sedentary not lying”. “Lying minus active” and “Lying minus sedentary not lying” is derived based on the following:

MLFHFN	Mean LF/HF (Avg over 5 min windows of lying down)	Use the sum of the means over each recording day (Day 1 + Day 2 + Day 3) divided by the total number of recording points over the 3 days (number Day 1+2+3) (number of lying periods of good enough quality to obtain HRV from)
VLFHFN	Var of LF/HF (Avg over 5 min windows of lying down)	Use the sum of the variances over each recording day (Day 1 + Day 2 + Day 3) divided by the total number of recording points over the 3 days (number Day 1+2+3) (number of lying periods of good

		enough quality to obtain HRV from)
MLFHFSD	Mean LF/HF (avg-stationary-day) Stationary = sedentary not lying	Derive 1 average value for each protocol time point, Use the sum of the means over each recording day (Day 1 + Day 2 + Day 3) divided by the total number of recording points over the 3 days (number Day 1+2+3) (number of 'sedentary not lying' periods of good enough quality to obtain HRV from)
VLHFSD	Var of LF/HF (avg-stationary-day) Stationary = sedentary not lying	Derive 1 average value for each protocol time point, Use the sum of the variances over each recording day divided by the total number of recording points (number of 'sedentary not lying' periods of good enough quality to obtain HRV from)

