MLHFAD	Mean LF/HF (avg-daytime activity)	Derive 1 average value for each protocol time point, Use the sum of the means over each recording day divided by the total number of recording points (number of active periods of good enough quality to obtain HRV from)
VLHFAD	Var of LF/HF (avg-daytime activity)	Derive 1 average value for each protocol time point, Use the sum of the variances over each recording day divided by the total number of recording points (number of active periods of good enough quality to obtain HRV from)
MRMSSD	Mean RMSSD (24 hr avg)	
VRMSSD	Var of RMSSD (24 hrs avg)	

- HRV effect of being upright = LF/HF stationary minus LF/HF lying
- HRV effect of activity = LF/HF active (MLHFAD) minus LF/HF lying (MLHFN)

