9.8. Appendix 8: Multiple Comparisons & Multiplicity

As this is an exploratory study, no adjustment will be made for multiple comparisons. Assessments about the correlation between endpoints will be made on the strength of the correlation coefficients.

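### The six LF/HF variables are derived as daily averages summed and divided by the count of usable recording points, so they are not averages and move inversely with that count

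*SAP*

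**What the plan says.** SAP Section 9.4.3 (Heart Rate Variability) defines six variables: the mean and the variance of LF/HF in each of three states (lying, sedentary not lying, active).

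- **Numerator.** All six rows sum the daily means or the daily variances. The two lying rows and the row for the sedentary-not-lying mean spell this out as one term for each of Days 1, 2 and 3.
- **Divisor.** All six rows divide by the total number of recording points. For the active mean: "Use the sum of the means over each recording day divided by the total number of recording points (number of active periods". For lying, the points are explained as the "number of lying periods of good enough quality to obtain HRV from".
- **Daily value.** The lying mean is labelled "Mean LF/HF (Avg over 5 min windows of lying down", so it is an average before the rule is applied. The header of the block says that all LF/HF metrics use 5-minute windows.
- **Stated aim.** The four rows for sedentary not lying and active begin "Derive 1 average value for each protocol time point".
- **Same appendix, night-time rest.** For movement episodes per hour, rest efficiency and the fragmentation index, the summed daily values are divided by the "actual number of recording periods at each time point".
- **Contrasts.** Section 2.2 lists "Mean and variance for HRV effect of activity = LF/HF active minus LF/HF lying", and the corresponding upright effect. Section 9.4.3 builds both from the variables above.
- **Data quality.** The minimum-count rule in Section 7.1.1 is headed "Heart Rate Variability (24 hour endpoints only)" and is applied to RMSSD. No minimum is set for LF/HF.

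**The concern.** A sum of daily averages has one term per day, so it becomes an average when divided by the number of days. Dividing it by the number of usable points removes the count a second time. The derived variable then mixes autonomic function with the amount of usable recording in that state.

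That mixture matters in this study. Usable points in a state depend on the time spent in it, on wear and on signal quality, and the times spent active, lying and sedentary are themselves studied as markers of progression. An association between derived LF/HF and ALSFRS-R could therefore reflect posture time or wear. Section 9.8 makes no multiplicity adjustment and says: "Assessments about the correlation between endpoints will be made on the strength of the correlation coefficients". A correlation created or hidden by the derivation would feed directly into that judgement.

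Outputs affected: Tables 2.105–2.108, 2.116–2.119, 2.127, 2.129 and 2.131; Figures 2.65, 2.66, 2.71, 2.72, 2.77, 2.79 and 2.81; and the derived values in Listings 58 and 61.

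**Working it through.** The SAP states no result for these variables, so there is no figure to reproduce. The algebra uses only the written rule. LF/HF levels, point counts and simulation inputs below are assumptions.

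**1. What the rule computes.** Let m_d be the daily mean, n_d the usable points on day d, and D the number of days.

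SAP rule = Σm_d / Σn_d = (Σm_d / D) / (Σn_d / D) = mean of the daily means ÷ mean usable points per day.

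This equals an average LF/HF only when there is, on average, one usable point per day.

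**2. Scale.** LF/HF 2.0 on each of 3 days, so the numerator is 6:

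| Points/day | SAP rule | Proper average |
|---|---|---|
| 10 | 6/30 = 0.20 | 2.0 |
| 40 | 6/120 = 0.05 | 2.0 |
| 100 | 6/300 = 0.02 | 2.0 |

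**3. Change over time with LF/HF constant.** The relative rate of decline reduces to (baseline points ÷ visit points) − 1.
- 40 to 80 points per day: 0.025/0.05 − 1 = −50%.
- 40 to 20 points per day: 0.10/0.05 − 1 = +100%.

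**4. Contrasts.**
- Equal LF/HF of 2.0, with 15 sedentary and 60 lying points per day: 6/45 − 6/180 = +0.10. The true upright effect is 0.
- Active 3.0 and lying 2.0, with 40 and 20 points per day: 9/120 − 6/60 = −0.025. The true effect is +1.0.
- When the true effect is positive, the sign reverses whenever n_active/n_lying exceeds m_active/m_lying.

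**5. Uneven days.** Daily means 1.5, 2.0 and 3.0 with 60, 40 and 20 points:
- SAP rule: 6.5/120 = 0.054
- Count-weighted: (90 + 80 + 60)/120 = 1.92
- Plain mean of days: 6.5/3 = 2.17

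**6. Variances.** Daily variances of 0.5 with 40 points per day: the SAP rule gives 1.5/120 = 0.0125; pooling within days gives 0.5.

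**7. Induced correlation with ALSFRS-R when the true correlation is 0.**
- *Simple correlation.* 400,000 draws; log-normal counts and LF/HF, each with a CV of 30% or 50%; LF/HF independent of ALSFRS-R.
  - Counts correlated −0.3 to −0.7 with ALSFRS-R: about +0.14 to +0.55.
  - Counts correlated +0.3 to +0.7: about −0.15 to −0.55.
  - Counts uncorrelated with ALSFRS-R: 0.
- *Within-subject correlation.* 2,000 simulated studies of 20 subjects; 13 four-weekly points; ALSFRS-R falling by 10 (SD 5) over 48 weeks; within-subject CV of 30% for LF/HF and 20% for counts; visit-to-visit ALSFRS-R noise between 0 and 2 points. The ranges reflect that noise:

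| Change in usable points over 48 weeks | Induced correlation |
|---|---|
| −50% | −0.40 to −0.46 |
| −25% | −0.19 to −0.22 |
| +25% | +0.15 to +0.18 |
| +50% | +0.26 to +0.30 |
| +100% | +0.40 to +0.46 |

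In the same runs, the correctly averaged LF/HF gave 0.00.

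**The case against.** The strongest reply is that the authors meant a count-weighted average and wrote it in shorthand. A total-count divisor is right when the numerator is a total over points. The derivation of average movement-episode duration in the same appendix divides by a total count for the stated purpose of greater accuracy. That intent is plausible. But the numerator as written has one term per day, and nowhere are daily values multiplied by their counts. A programmer following the text would code the wrong quantity.

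Other points on that side:

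- **The divisor is partly inferred.** The LF/HF rows speak of periods of adequate quality. Section 7.1.1 equates data points with 5-minute windows, but only for RMSSD, so a period could mean a posture bout. This makes the illustrative counts uncertain; the identity in step 1 holds for any count.
- **The count is bounded above.** If points are windows, there are at most 288 per 24 hours, or 264 after the charging allowance. There is still no lower limit for LF/HF.
- **The error may be noticed.** Section 7.1.2 and Listing 64 provide for listing the vendor's HRV data, so a many-fold discrepancy could be seen. That helps detection; it does not correct the rule.
- **The study is exploratory, without a primary endpoint.** This limits the consequences, but the LF/HF results would still be unusable if coded literally.

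**Conclusion.** The concern holds, and the rule must be fixed before the analysis is programmed. As written, all six LF/HF variables equal the intended average divided by the mean number of usable points per day. That conclusion follows from the text alone.

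Two consequences need no assumption about how counts relate to ALSFRS-R: the values are off the LF/HF scale, and the posture contrasts subtract quantities divided by different counts. The effect on the correlations does depend on that relation, which the SAP does not give. It is zero for the simple correlation if counts and ALSFRS-R are unrelated. Under the assumed inputs it reaches about 0.55 in either direction for the simple correlation and about 0.46 within subjects. These figures show what could happen; they do not estimate the bias in this trial.

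The RMSSD part of the heart rate variability objective, and the actigraphy and speech analyses, are outside this finding.

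**What to change.** In SAP Section 9.4.3, replace the divisor rule in all six LF/HF rows.

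- **Means:** use either Σ(n_d × m_d) / Σn_d, or Σm_d / number of recording days, and state which.
- **Variances:** use a matching rule, for example Σ((n_d − 1) × v_d) / Σ(n_d − 1), and note that this describes within-day variance only.
- **Divisor:** say whether a recording point is a 5-minute window.

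The plain mean of days needs no new data. The weighted form needs the usable count per state and day, which the present rule already uses. The cost is a wording change and a few lines of derivation code.

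Two minor clarifications can be made in the same edit; neither drives the severity. Use one direction for the posture contrasts: Section 2.2 subtracts lying, while the introduction to the HRV block in Section 9.4.3 and the programming notes for Tables 2.105–2.108 and 2.116–2.119 start from lying, which changes only the sign. For average movement-episode duration, state that the summed values are total movement times per night; if they are nightly averages, the same error arises there.
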